9.1. Efficacy Assessments

9.1.1. Primary Efficacy Assessments

Patient Diary

Patients will be introduced to the eDiary at Visit 1 and trained on the use of the eDiary at Visit 2. Efficacy data will be collected in the eDiary. Patients will record the date and time at which their migraine headache starts. They will also record severity and the date and time of taking the study drug. Patients will be asked to assess their headache severity at specified time points: 0 (pre dose), 0.5, 1, 1.5, 2, 3, 4 and 24, and 48 hours postdose using the IHS 4-point headache severity rating scale (0 = no pain, 1 = mild pain, 2 = moderate pain, and 3 = severe pain). The eDiary assessments are listed in Appendix 5.

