9.1.2. Secondary Efficacy Assessments

Patient Diary

Other efficacy data will also be collected in the eDiary.

At the time points, 0 (pre dose), 0.5, 1, 1.5, 2, 3, 4, 24, and 48 hours, patients will assess the presence or absence (yes or no) of accompanying symptoms: photophobia, phonophobia, nausea, and vomiting. At time 0 (pre dose) patients will select from the accompanying symptoms present (from nausea, phonophobia, or photophobia only) the one that is the most bothersome to them.

Patients will also be asked to record the time of meaningful relief and the time at which they become headache pain free. At 2 and 24 hours after the study drug, patients will be asked to record their Patient Global Impression of Change (PGI-C) using a 7-point scale (very much better, much better, a little better, no change, a little worse, much worse, and very much worse). The eDiary assessments are listed in Appendix 5.

Patients will record details of AEs, concomitant medication use, and any other relevant information in the patient's paper diary and these will be reviewed at the next visit.

Recording Use of Rescue/Recurrence Medication: Refer to Section 7.2.1.1 for details.

Migraine Quality of Life Questionnaire (MQoLQ): The 24-hour Migraine Quality of Life Questionnaire (24-hr MQoLQ) has been specifically developed to measure the Health-Related Quality of Life of patients with migraine within a 24-hour period after having taken migraine medication. The 24-hour MQoLQ is a 15-item, self-administered questionnaire. The items cover 5 domains (work functioning, social functioning, energy and vitality, feelings and concerns, and migraine symptoms) (Hartmaier et al. 1995; Santanello et al. 1995, 1997). Each domain consists of 3 questions answered on a 7-point scale where 1 indicates maximum impairment and 7 indicating no impairment. A domain score is calculated by summing the responses to the 3 questions and the domain score ranges from 3 to 21. The questionnaire will be administered 24 hours after the study drug.

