- For Kaplan-Meier analysis, corresponding figures will be created. Quartiles and rates, along with 95% CIs, were estimated using the Kaplan-Meier method. Corresponding 95% CIs were estimated using the methods of Brookmeyer and Crowley, and Greenwood, respectively.
- When baseline usage of preventive medications to reduce the frequency of migraine (Yes/No) is included in a statistical model, it is based on CRF, not IWRs.
- Efficacy analyses are based on eDiary data, unless otherwise specified.
- Comorbid condition is based on Visit 1.
- When median is used for subgroup analysis (e.g. SUB4, body weight), the median is based on mITT population.

We will use the following analysis population rules unless otherwise specified (see population definitions in Section [5.3](#)):

- Protocol deviation summary will be based on all randomized and mITT/ITT.
- Demographics and Baseline characteristics will be based on mITT/ITT/safety population (SP).
- Efficacy analyses [T1], [T2], [T3], and MBS will be based on mITT/ITT/per-protocol set (PPS).
- Other efficacy and health outcome will be based on ITT.
- Safety analyses (e.g., AE, laboratory assessments/vital signs), medication, and treatment compliance/eDiary compliance will be based on SP.

When continuous variables, including change from baseline scores, is summarized using descriptive statistics, it will show n (number of subjects with available data), mean, median, standard deviation, minimum, and maximum.

Minimum and maximum values will be presented to the same precision as the raw data. Mean and median will be presented to one more decimal place than the raw data. Standard deviation will be presented to two more decimal places than the raw data. P-values will be presented to three decimal places.

Categorical variables will be summarized using counts and percentages. Unless otherwise specified, percentages will be calculated using the numbers of subjects in the summarized

population in each treatment group as denominators. Percentages will be presented with a precision of 1 digit after the decimal.

Observations collected prior to dosing will serve to determine a baseline measurement; the latest available measurement prior to dosing will be used as the baseline. For data collected by eDiary, the baseline values will be the Hour-0 assessment times identified in the eDiary.

SAS® software (version 9.2 or higher) will be used to perform most or all statistical analyses.

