Abbreviations: 2KEY= key secondary analysis; 2ND= other secondary analysis; ANOVA= Analysis of Variance; CA= Cochran-Armitage trend test; CMH= Cochran-Mantel-Haenszel test; EQ-5D-5L = EuroQol 5-dimension 5-level scale; h= hour; HRQoL = Health-Related Quality of Life; ITT= intent-to-treat population ; KM= Kaplan-Meier analysis; LOGISTIC= logistic regression; MBS = the most bothersome symptom; MQoLQ = Migraine Quality of Life Questionnaire; mITT= modified intent-to-treat population; NA= not applicable (descriptive statistics is used); OTH= exploratory analysis; PGI-C = Patient Global Impression of Change; PPS= per protocol set population; PRIM= primary analysis

Definition of analysis used in [Table LAIH. 5.3](#) are listed below:

Pain Free

It is defined as reduction in headache severity from moderate (2) or severe (3) at baseline to none (0) at indicated assessment time.

Pain Relief

It is definition as reduction in headache severity from moderate (2) or severe (3) at baseline to mild (1) or none (0).

MBS-Free

MBS-free is defined as the absence of the associated symptom of migraine (either nausea, phonophobia, or photophobia) at the indicated assessment time that was identified pre-dose as the most bothersome symptom. Subjects who record that no symptoms were present at time of dose are excluded from the MBS analysis.

Migraine Symptoms Present at Assessment Times (Nausea, Phonophobia, Photophobia, Vomiting)

This is 4 separate analysis of Nausea, Phonophobia, Photophobia, Vomiting, regardless of corresponding baseline values.

MBS-Free by Chosen Symptom: (Nausea, Phonophobia, Photophobia)

This is 3 separate subgroup analysis of MBS. For example, the nausea analysis is based on those who chose “nausea” as the most bothersome symptom at baseline.

Time to Headache Pain Free Through 48 Hours Post-Dose

It is defined as a reduction in headache severity to pain free at any assessment time for the first time through 48 hours after the dose.

Time to Headache Pain Relief Through 48 Hours Post-Dose

It is defined as a reduction in headache severity to pain relief at any assessment time for the first time through 48 hours after the dose.

Time to MBS-Free Through 48 Hours Post-Dose

It is defined as the absence of the associated symptom of migraine, (either nausea, phonophobia, or photophobia) that was identified pre-dose as the most bothersome symptom, at any assessment time for the first time through 48 hours after the dose.

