Time to MBS-Free by Chosen Symptom Through 48 Hours Post-Dose: (Nausea, Phonophobia, Photophobia)

This is 3 separate subgroup analysis of “Time to MBS Free Through 48 Hours Post-Dose”. For example, the nausea analysis is based on those who chose “nausea” as the most bothersome symptom at baseline.

Disability

Disability is measured on a four-point scale: not at all (0); mild interference (1); marked interference (2); and need complete bed rest (3). Proportion of patients with score = 0 for each group at each post baseline time point is analyzed. Note that patients with 0 severity at baseline will be excluded from the analysis. In addition, frequency of each category will be summarized.

Incidence of Rescue or Recurrence Medication Use

The analysis is conducted for 3 time frames, depending on rescue or recurrence medication dose time after the treatment intake: [0h<=dose<2h], [2h<=dose<24h], and [24h<=dose<=48h].

A subject is defined to have used rescue or recurrence medication if at least one medication is used during the time frame. Definitions of rescue/recurrence medication are in PROTOCOL Section 7.2.1.1.

Incidence of Headache Recurrence Through 24/48 Hours Post-Dose

It is defined that patients with pain-free at 2 hours post-dose becomes mild (1) or more before or at 24/48 hours post dose. We consider missing data as “non-recurrence” at each time point.

PGI-C

PGI-C is measured on a seven-point scale from “very much better” to “very much worse.” Responder is defined as top two categories, "very much better" and "much better". In addition, frequency of each category will be summarized.

Sustained Pain Free at 24 hours and 48 hours

Sustained Pain-Free is defined as experiencing headache pain-free at two hours after the dose and at the indicated assessment time, having not used any rescue/recurrence medications after the dose up to the assessment timing.

Time to No Disability Through 24 Hours

Disability is measured on a four-point scale: not at all (0); mild interference (1); marked interference (2); and need complete bed rest (3).

No Disability timing is defined as the first time when severity becomes 0. Note that patients with 0 severity at baseline will be excluded from the analysis.

Summary of Symptom-Free at Assessment Times (Nausea, Phonophobia, Photophobia, Vomiting)

This is 4 separate analysis of the symptom.

Total Migraine Freedom

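### Kaplan-Meier quartiles for IDs 7-10 and 16 print as 24 h whenever they fall in the 4-24 h (disability: 2-24 h) diary gap, although the data give only an interval

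*SAP*

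**What the plan says.** SAP 5.4 sets one method for the Kaplan-Meier analyses: "Quartiles and rates, along with 95% CIs, were estimated using the Kaplan-Meier method", with Brookmeyer-Crowley limits for quartiles and Greenwood limits for rates. In Table LAIH. 5.3, IDs 7, 8, 9 and 16 are other secondary and ID 10 is exploratory. All use the ITT population.

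SAP 5.6.3 dates each event by a scheduled assessment:
- ID 7 (pain free): "a reduction in headache severity to pain free at any assessment time for the first time through 48 hours".
- ID 8 (pain relief): "a reduction in headache severity to pain relief at any assessment time for the first time through 48 hours".
- ID 9 (free of the most bothersome symptom, MBS): absence of that symptom "at any assessment time for the first time through 48 hours after the dose". ID 10 is the same by chosen symptom.
- ID 16 (no disability): "No Disability timing is defined as the first time when severity becomes 0".

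Headache severity is entered at "0 (pre dose), 0.5, 1, 1.5, 2, 3, 4 and 24, and 48 hours postdose" (Protocol 9.1.1). Accompanying symptoms follow the same times. Disability is rated at 0, 0.5, 1, 2 and 24 h only (both Protocol 9.1.2).

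SAP 5.4.1 censors these analyses at the first missing entry, at rescue or recurrence medication, or at the last possible evaluation, whichever is earliest. Neither document names an interval-censored method or a rule for reporting a quartile that falls between 4 h (or 2 h) and 24 h.

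Separately, Protocol 9.1.2 states: "Patients will also be asked to record the time of meaningful relief and the time at which they become headache pain free". These recorded times feed IDs 20 and 21, both exploratory, for which 6 h and 8 h results are planned.

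**The concern.** A patient who is not pain free at 4 h and is pain free at 24 h became so at some point in a 20 h window. Ordinary Kaplan-Meier treats the entry time as the event time, so the whole step in the curve sits at 24 h. The curve is sound where it is read at scheduled times. A quartile, or a Brookmeyer-Crowley limit, that falls in the window takes its value from the diary schedule and not from when patients responded. The schedule is fixed, but printing 24 h as a point estimate is a choice.

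What is at stake is the comparison of arms. If one arm passes 50% just before 4 h and its neighbour just after, the table shows 4 h against 24 h for two nearly identical response times. The SAP does not say whether nominal or actual entry times are used, but the gap remains either way.

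**Working it through.** **Plan's own figures.** The documents state no median for these analyses. The 2 h rates and arm sizes used below (Protocol 10.1.1, SAP 5.2) were checked against the stated power. Recalculation gives 95.0% for placebo v 200 mg (stated 93.6%), 94.9% for the trend test (94.9%), 92.2% for placebo v 100 mg pain relief (91.2%) and 86.8% in total (85.6%). All are within 2 points.

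**Rule.** The printed quartile is the first scheduled time at which cumulative first response F reaches it. A median prints as 24 h only if F is below 50% at the last entry before the gap and has reached 50% by 24 h.

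**Pain relief (ID 8).** Planning rates at 2 h are 59.0%, 64.8% and 65.0% in the active arms. All exceed 50%, so those medians are at most 2 h whatever the distribution. Placebo, at 47.7%, needs 2.3 more points by 4 h. With constant hazard the medians are 2.1 h (shown as 3), 1.6 (2), 1.3 (1.5) and 1.3 (1.5) for placebo, 50, 100 and 200 mg. The placebo upper quartile, 4.3 h, would print as 24 h.

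**Pain free (ID 7).** Assumption: constant hazard λ = −ln(1 − p)/2, with p the planning 2 h rate. Then F(4) = 1 − (1 − p)², median = ln 2/λ and upper quartile = ln 4/λ.

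| Arm | p | λ per h | F(4 h) | Median → shown (h) | Upper quartile → shown (h) |
|---|---|---|---|---|---|
| Placebo | 21.3% | 0.1198 | 38.1% | 5.8 → 24 | 11.6 → 24 |
| 50 mg | 28.6% | 0.1684 | 49.0% | 4.1 → 24 | 8.2 → 24 |
| 100 mg | 31.4% | 0.1884 | 52.9% | 3.7 → 4 | 7.4 → 24 |
| 200 mg | 38.8% | 0.2455 | 62.5% | 2.8 → 3 | 5.6 → 24 |

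Placebo v 200 mg: 5.8 − 2.8 = 3.0 h is displayed as 24 − 3 = 21 h. 50 v 100 mg: 4.1 − 3.7 = 0.4 h is displayed as 24 − 4 = 20 h.

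**Confidence limit.** At 100 mg with the planned 190 patients and no censoring, S(4) = 0.686² = 0.471 and its standard error is √(0.471 × 0.529/190) = 0.036. Since |0.471 − 0.5| = 0.029 is less than 1.96 × 0.036 = 0.071, the 4 h entry lies inside the interval and the upper limit prints as 24 h. So an arm whose median escapes the gap can still have a limit in it.

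**Shape.** With a Weibull of shape k, the median is 2 × [ln 2/(−ln(1 − p))]^(1/k). Median → shown, in hours:

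| k | Placebo | 50 mg | 100 mg | 200 mg |
|---|---|---|---|---|
| 0.5 | 16.8 → 24 | 8.5 → 24 | 6.8 → 24 | 4.0 → 4 |
| 0.75 | 8.2 → 24 | 5.2 → 24 | 4.5 → 24 | 3.2 → 4 |
| 1.5 | 4.1 → 24 | 3.2 → 4 | 3.0 → 4 | 2.5 → 3 |
| 2 | 3.4 → 4 | 2.9 → 3 | 2.7 → 3 | 2.4 → 3 |

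The upper quartile also moves with shape. At k = 2 it prints as 24 h for placebo and 50 mg and as 4 h for 100 and 200 mg.

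**Sampling and rescue.** In 300 simulated trials per scenario (constant hazard, planned arm sizes, rescue censoring assumed in 0%, 30% or 60% of patients), the pain-free median printed as 24 h or later in 100% of runs on placebo, 57-61% at 50 mg, 18-20% at 100 mg and 0-1% at 200 mg. The pain-relief median never did.

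**Disability (ID 16) and MBS (IDs 9-10).** The documents give no rates for either. A disability median can print as 24 h only if fewer than half have responded by 2 h. For assumed 2 h rates of 20-45% and shapes 0.5 to 1.5, the underlying median is 2.2 to 19 h. For MBS the threshold is half by 4 h.

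**The case against.** The strongest reply is that the SAP openly defines IDs 7-9 as first response at an assessment, so 24 h is correct for the variable as defined and the risk is only one of interpretation. The time-course endpoint itself is the proportion at each time point, analysed by logistic regression and untouched by rounding. No test on medians is specified, and everything here lies outside the gatekeeping. For pain freedom, recorded times are already planned as ID 21. All of this stands, and it keeps the severity low. It does not justify printing a point estimate and a confidence limit that the data cannot locate within 20 to 22 h. ID 21 ranks below ID 7, and MBS and disability have no recorded-time version.

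A second reply concerns the size. The calculation extrapolates one 2 h rate per arm through an assumed distribution in which everyone eventually responds. The 2 h figure is also the proportion pain free at that time, and cumulative first response is at least as high. Both points stand.

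A reader might infer that medians are badly overstated in all five analyses, or that the displayed placebo v 200 mg gap would reliably be 20 to 21 h. The documents support neither. The planning rates rule this out for active-arm pain relief, there are no rates for MBS or disability, and at shape 2 the display is 4 h against 3 h. Nor is every response in the gap dated 24 h. Patients who take rescue medication or miss an entry are censored first, and a response lost before the 24 h entry is dated 48 h or never.

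**Conclusion.** The point holds in a limited form: a quartile or confidence limit that falls in a diary gap prints as 24 h when only an interval is known.

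At the planning rates with constant hazard:
- The placebo pain-free median is overstated by about 18 h (24 − 5.8).
- The 50 mg median may be overstated by about 20 h (24 − 4.1), but F(4 h) is so close to 50% that it could fall on either side.
- The upper pain-free quartile prints as 24 h in all four arms.
- The 100 and 200 mg pain-free medians are off by less than 0.4 h, and the pain-relief medians by less than 1 h.

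This rests on the reference study's 2 h rates and on the assumed shape. For shapes from 0.5 to 2, between three and none of the four pain-free medians land on 24 h. The disability and MBS effects are conditional.

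Kaplan-Meier rates at scheduled times and the primary and two key secondary tests are unaffected. This is a cheap improvement of low severity to other secondary and exploratory tables.

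**What to change.** In SAP 5.4 and 5.6.3, for IDs 7-10 and 16:
- Keep the estimated rates, with their Greenwood intervals, at the scheduled times.
- Report any quartile or confidence limit that falls in the gap as an interval (>4 to 24 h, or >2 to 24 h for disability), from an interval-censored (Turnbull) estimate or by an equivalent display rule.
- Present ID 21, the patient-recorded time to pain free, beside ID 7. Treat it as a companion and not a replacement: SAP Appendix 1 appears to place the recorded-time questions at the 48 h entry, so their precision is not established.
- Do not use ID 20 in place of ID 8. Meaningful relief is a different outcome from a fall in severity from moderate or severe to mild or none.

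The cost is SAP wording and a different procedure or footnote for a few tables. Data collection, sample size and gatekeeping do not change. The downside is that some medians appear as ranges.

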5.4.1. Handling of Missing Values

Subjects who fail to record information at an analysis time point will have that value considered missing in the respective table (hence, no imputation), unless otherwise specified.

Pain free, Pain relief, and MBS analysis are exceptions to this. Missing value at a particular time point is considered as “non-responder.”

Note that if a patient takes a rescue/recurrent medication at some postbaseline timepoint (see Section 5.4), then all evaluation after that timepoint becomes nonresponder, even if the evaluation is missing.

For time-to-event analyses (Time to Meaningful Pain Relief Through 48 Hours, Time to Pain Free Through 48 Hours), patients will be censored at the first time when rescue/recurrent medication are used or at 48 hours, whichever the earliest.

For the other time-to-event analyses (Kaplan-Meier analyses), the patient will be censored at the first missing evaluation time point or rescue/recurrent medication taken time (postbaseline), or the last possible evaluation point whichever the earliest, unless otherwise specified. For example, the last possible evaluation point of disability is at 24 hours.

A sensitivity analysis for missing data will be performed. (See Section 5.6.2).

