5.4.2. Derivation of eDiary Assessment Times for Efficacy and Exploratory Analysis

There will be some scenarios whereby responses appear to have been limited by the diary programming if questions are not answered during the programmed window.

One specific scenario is missing dose timing data. If the dose is reported taken in the CRF but the subject is not able to select the date and time in the diary, then the date of dose will be missing in diary data. In such cases, efficacy assessments will be considered as missing. However, for safety analysis, the dosing date and time in the CRF will be considered as the baseline timing.

Unless otherwise specified, if incomplete data or contradictions are found for other reasons, then such data will not be used for analysis. Such irregular cases will be listed.

e.g. If meaningful pain free time is before dosing time, then it is contradiction. This data will not be used for the meaningful pain free time analysis.

e.g. If there are two data record at a specific timepoint, then first data record is used for that time point and the other one will be discarded. In addition, all data recorded at subsequent timepoints will be discarded.

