5.6.3. Details of Efficacy Analyses

Table LAIH. 5.3 is the list of primary/ key secondary/ other secondary/ exploratory analysis with each analysis population, timeframe and analysis method.

Table LAIH. 5.3 Primary, Key Secondary, Other Secondary and Exploratory Efficacy Variables and Analysis Methods

ID	Type	efficacy variables	POP	Timeframe	Analysis
1	PRIM /2 ND	Headache Pain Free	mITT/ ITT/ PPS	up to 48h	LOGISTIC
2	2KEY	Pain Free Trend Test	mITT/ ITT/ PPS	2h	CA
3	2KEY /2ND	Headache Pain Relief	mITT/ ITT/ PPS	up to 48h	LOGISTIC
4	2 ND	MBS-Free	mITT/ ITT/ PPS	up to 48h	LOGISTIC
5	2 ND	Migraine Symptoms Present at Assessment Times (Nausea, Phonophobia, Photophobia, Vomiting)	ITT	up to 48h	LOGISTIC
6	OTH	MBS-Free by Chosen Symptom: (Nausea, Phonophobia, Photophobia)	ITT	up to 48h	LOGISTIC
7	2 ND	Time to Headache Pain Free Through 48 Hours Post-Dose	ITT	up to 48h	KM
8	2 ND	Time to Headache Pain Relief Through 48 Hours Post-Dose	ITT	up to 48h	KM
9	2 ND	Time to MBS-Free Through 48 Hours Post-Dose	ITT	up to 48h	KM
10	OTH	Time to MBS-Free by Chosen Symptom Through 48 Hours Post-Dose: (Nausea, Phonophobia, Photophobia)	ITT	up to 48h	KM
11	2 ND	Disability	ITT	0.5h/1h/2h/24h	LOGISTIC

12	OTH	Incidence of Rescue or Recurrence Medication Use	ITT	[0h-2h]/ [2h-24h]/ [24h-48h]	LOGISTIC
13	OTH	Incidence of Headache Recurrence Through 24/48 Hours Post-Dose	ITT	2h< recurrence <=24h 2h< recurrence <=48h	LOGISTIC
14	2 ND	PGI-C	ITT	2h/24h	LOGISTIC
15	2 ND	Sustained Pain Free at 24 Hours and 48 Hours	ITT	24h/48h	LOGISTIC
16	2 ND	Time to No Disability Through 24 Hours	ITT	up to 24h	KM
17	OTH	Summary of Symptom-Free at Assessment Times (Nausea, Phonophobia, Photophobia, Vomiting)	ITT	up to 48h	LOGISTIC
18	OTH	Total Migraine Freedom	ITT	up to 48h	LOGISTIC
19	OTH	Modified Sustained Pain Free at 24 Hours and 48 Hours	ITT	24h/48h	LOGISTIC
20	OTH	Time to Meaningful Pain Relief Through 48 Hours	ITT	up to 48h (including 6h/8h)	KM
21	OTH	Time to Pain Free Through 48 Hours	ITT	up to 48h (including 6h/8h)	KM
22	2 ND	Change from Baseline of EQ-5D-5L in Index Score	ITT	24h	ANOVA
23	2 ND	Change From Baseline of EQ-5D-5L in Visual Analog Scale	ITT	24h	ANOVA
24	2 ND	HRQoL Measured by MQoLQ in 5 Domains	ITT	24h	ANOVA
25	2 ND	Treatment Satisfaction	ITT	48h	CMH

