If patients are pain free and are not experiencing any other migraine symptoms (i.e. nausea, photophobia, phonophobia, or vomiting), then they are total migraine free.

Modified Sustained Pain Free at 24 hours and 48 hours

Modified Sustained Pain-Free is defined as experiencing headache pain-free at two hours after the dose and no moderate or severe pain at the indicated assessment time, having not used any medications to treat migraine after the dose up to the assessment timing. Note that if a patient has missing evaluation at 24 hours, then he is excluded from the analysis instead of setting his response as nonresponder. The same is true at 48 hours evaluation.

Time to Meaningful Pain Relief Through 48 Hours

Meaningful Pain Relief timing is defined as the time when the corresponding eDiary question is answered as Yes.

Time to Pain Free Through 48 Hours

Pain Free timing is defined as the time when the corresponding eDiary question is answered as Yes.

Change from Baseline of EQ-5D-5L in Index Score

It is based on the EQ-5D Health Status Index Score. The Japan specific tariffs (Japanese population-based index value) for the EQ-5D Health Status Index Score is used. Change from baseline is based on Baseline (0 hour) and post-baseline (24 hours).

Change from Baseline of EQ-5D-5L in Visual Analog Scale

The change of EQ-5D-5L visual analog scale is based on Baseline (0 hour) and post-baseline (24 hours) from the onset of dosing.

HRQoL Measured by MQoLQ in 5 Domains

There are 5 domains in MQoLQ. Each domain will be analyzed separately: work functioning, social functioning, energy and vitality, feelings and concerns, and migraine symptoms. Each domain consists of 3 questions answered on a 7-point scale where 1 indicates maximum impairment and 7 indicating no impairment. A domain score is calculated by summing the responses to the 3 questions and the domain score ranges from 3 to 21. The response variable in this analysis is raw values at 24 hours.

Treatment Satisfaction

There are 4 questions. Each question will be analyzed separately. Distribution of responses and proportion of patients with agree or strongly agree will be summarized for each treatment group:

- the patient's level of satisfaction (ranging from extremely dissatisfied to extremely satisfied)
- their willingness to take this treatment again (ranging from strongly disagree to strongly agree)

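### Times to meaningful relief and to pain freedom (IDs 20 and 21) treat time after the diary stops as observed and event-free up to 48 h, so their cumulative rates can be too low

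*SAP*

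**What the plan says.** SAP 5.4.1 has two censoring rules.

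- One covers exactly two analyses: "For time-to-event analyses (Time to Meaningful Pain Relief Through 48 Hours, Time to Pain Free Through 48 Hours". In these, "patients will be censored at the first time when rescue/recurrent medication are used or at 48 hours, whichever the earliest". A missing diary entry is not a reason for censoring.
- The other covers the remaining Kaplan-Meier analyses, in which "the patient will be censored at the first missing evaluation time point or rescue/recurrent medication taken time (postbaseline"), or at the last possible evaluation if that is earlier. Because "Time to Headache Pain Free Through 48 Hours Post-Dose" (ID 7) is not one of the two named analyses, it falls here.

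The events are defined in SAP 5.6.3. For ID 20, "Meaningful Pain Relief timing is defined as the time when the corresponding eDiary question is answered as Yes". For ID 21, "Pain Free timing is defined as the time when the corresponding eDiary question is answered as Yes". ID 7 instead uses the scheduled severity scores: "a reduction in headache severity to pain free at any assessment time for the first time through 48 hours after the dose".

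Table LAIH. 5.3 classes IDs 20 and 21 as exploratory and ID 7 as other secondary, all on the ITT population. According to the revision history, version 2 added 6 h and 8 h results for IDs 20 and 21. SAP 5.4 plans Kaplan-Meier quartiles and rates with confidence intervals.

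**The concern.** In IDs 20 and 21 the event exists only if the patient answers Yes in the eDiary. Once the patient stops using it, an event can no longer be seen. The rule nevertheless keeps the patient in the risk set with no event until rescue or 48 h, so it counts time in which nothing could be observed as follow-up. The SAP gives no reason for treating these two analyses differently from the other Kaplan-Meier analyses.

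At stake are the cumulative rates and medians of two descriptive analyses. Each patient who stopped and then had the event enters as a patient who did not have it, which lowers the cumulative curve and delays the median.

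**Working it through.** **1. One patient under both rules.** The last eDiary entry is at 2 h; no Yes, no pain-free score, no rescue. The next scheduled entries are at 3, 4, 24 and 48 h (SAP Appendix 1).

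| Analysis | Follow-up ends | Time counted after the last entry |
|---|---|---|
| ID 7 | 3 h, first missing evaluation | 1 h |
| IDs 20, 21 | 48 h | 48 − 2 = 46 h |

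**2. Does anything else in the SAP repair this?** No. The missing-data sensitivity analysis in 5.6.2 covers T1, T2, T3 and MBS only. ITT membership (5.3) requires just one postdose severity or symptom assessment, so patients with sparse diaries stay in.

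**3. Size, by illustration.** The SAP states no figure to reproduce. Let F(t) be the true cumulative proportion with the event. Let a share d of patients stop at time s, unrelated to outcome, with no rescue. Carrying them event-free to 48 h gives

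F(t) − d × [F(t) − F(s)] for t > s.

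Inputs:

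- From the SAP: 31.4% pain free at 2 h (100 mg planning rate) and n = 190 (5.2).
- Assumed: 75% by 24 h; Weibull shape; s equally likely to be 1, 2, 3 or 4 h; d from 2% to 20%.

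Weibull F(t) = 1 − exp(−λt^k):

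- −ln(0.686) = 0.377 and −ln(0.25) = 1.386
- k = ln(1.386/0.377)/ln(24/2) = 0.524
- λ = 0.377/2^0.524 = 0.262

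F(1), F(2), F(3) and F(4) are 23.1%, 31.4%, 37.3% and 41.8%; their mean is 33.4%. The shortfall is d × [F(t) − 33.4%], in points, from unrounded values:

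| t | F(t) | F(t) − 33.4% | d = 2% | d = 5% | d = 10% | d = 20% |
|---|---|---|---|---|---|---|
| 6 h | 48.8% | 15.5 | 0.3 | 0.8 | 1.5 | 3.1 |
| 8 h | 54.1% | 20.7 | 0.4 | 1.0 | 2.1 | 4.1 |
| 24 h | 75.0% | 41.6 | 0.8 | 2.1 | 4.2 | 8.3 |
| 48 h | 86.4% | 53.0 | 1.1 | 2.6 | 5.3 | 10.6 |

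A simulation of 400,000 patients at d = 10% agrees: 52.0% at 8 h, 70.8% at 24 h and 81.0% at 48 h. Censoring at the last entry returned the true rates to within 0.1 point.

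The estimated median is where F(t) = (0.5 − 0.334d)/(1 − d). It moves from 6.4 h to 6.7 h at d = 5% and to 7.1 h at d = 10%.

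For scale, the standard error at n = 190, ignoring censoring, is √(0.541 × 0.459/190) = 3.6 points at 8 h and √(0.75 × 0.25/190) = 3.1 points at 24 h.

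**4. The opposite assumption.** Suppose no patient who stops ever has the event. At d = 10% the true 24 h rate is then 75.0 − 4.2 = 70.8%, which the current rule estimates exactly. Censoring at the last entry gives 75.0%, which is 4.2 points too high. Taken alone, then, the current rule is correct or too low, never too high.

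**The case against.** Several points on the other side carry weight.

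- **Direction.** A reader might infer that the curves are too low. The documents do not show this: they give neither a drop-off rate nor the outcome of patients who stop. Rescue censoring also acts on these curves. If rescue is taken mainly by non-responders, it pushes the cumulative curve up. Both rules censor at rescue, so it does not explain the difference between them, but the net direction is open.
- **Consistency with the SAP's convention.** SAP 5.4.1 counts missing pain-free and pain-relief values as non-response, and carrying patients forward event-free resembles that. It is a defensible choice, but the SAP does not present the rule as such, and the other Kaplan-Meier analyses do not follow it.
- **ID 7 is not a like-for-like standard.** ID 20 is a different event. IDs 7 and 21 would differ even with complete diaries, since one uses scheduled scores and the other a patient-recorded time. ID 7's rule also discards pain freedom observed after a single missed entry, so copying it would be no clear improvement.
- **How the times are captured.** SAP Appendix 1 marks both time questions in the 48 h column, possibly through a lost merged cell, while 5.6.3 reads as entry when the event occurs. If they are answered only at 48 h, a patient without that entry reports no time at all. At d = 10% the current rule would then give 0.9 × 54.1 = 48.7% at 8 h, and censoring at the last entry 51.7%, against a true 54.1%. At 2 h, censoring at the last entry would give 28.5% against 31.4%. Both are low, and the proposed change is then only a partial repair.
- **Discarded times.** A reader might infer that a patient whose contradictory time is dropped under 5.4.2 is also carried to 48 h. The text says only "This data will not be used for the meaningful pain free time analysis" and that such cases are listed. Leaving the patient out is at least as natural a reading.
- **Comparison with placebo.** Bias between arms, for example through somnolence, is possible but not shown. No between-arm test is specified for these curves, and 5.5.5 already summarises diary compliance by time point and treatment, so unequal drop-off would be visible.

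**Conclusion.** The point holds as a minor one. SAP 5.4.1 counts unobserved time as event-free follow-up in IDs 20 and 21, unlike every other Kaplan-Meier analysis, and no sensitivity analysis covers it. The cumulative rates can be too low and the medians too late; whether they are depends on what happened to patients after they stopped.

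Under the stated assumptions the 8 h and 24 h rates are about 1.0 and 2.1 points low at 5% drop-off, and 2.1 and 4.2 points low at 10%. At 5% both shifts are smaller than one standard error; at 10% only the 24 h shift exceeds it. The size rests on an assumed drop-off rate, stopping unrelated to outcome, an assumed 75% by 24 h, no rescue, and times entered as events occur.

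Only exploratory, descriptive results are affected. T1, T2, T3 and the sample size do not depend on this rule.

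**What to change.** In SAP 5.4.1, for IDs 20 and 21 and patients with no Yes, censor at the earlier of first rescue/recurrence medication and the last completed eDiary entry, using 48 h only when the 48 h entry is present. First confirm from the eDiary specification that the two time questions are answered as events occur, and say so in 5.6.3, since the change is sound only on that condition. Keep the current rule as a sensitivity analysis, because stopping may be related to outcome; the two results then show how much the handling of stopped diaries matters. It would also help to state in 5.4.2 whether a patient whose time is discarded leaves the analysis, and to report how many there are.

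The cost is a few lines of SAP text, a small programming change and one extra set of curves. Fewer patients remain at risk at late times, so intervals there are slightly wider.
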